17.3 Informed Consent

The informed consent form must be written in a manner that is understandable to the subject population. Prior to its use, the informed consent form must be approved by the IRB.

The Principal Investigator or authorized key personnel will discuss with the potential subject the purpose of the research, methods, potential risks and benefits, subject concerns, and other study-related matters. This discussion will occur in a location that ensures subject privacy and in a manner that minimizes the possibility of coercion. Appropriate accommodations will be made available for potential subjects who cannot read or understand English or are visually or audibly impaired. Potential subjects will have the opportunity to contact the Principal Investigator or authorized key personnel with questions and will be given as much time as needed to make an informed decision about participation in the study.

Before conducting any study-specific procedures, the Principal Investigator must obtain written informed consent from the subject or a legally acceptable representative. The original informed consent form will be stored in a study-specific informed consent binder, and a copy of the informed consent form will be provided to the subject. The Principal Investigator and the study team are responsible for asking the subject whether the subject wishes to notify his/her primary care physician about participation in the study. If the subject agrees to such notification, the Principal Investigator will inform the subject's primary care physician about the subject's participation in the clinical study.

17.4 Privacy, Confidentiality, and Data Storage

The Principal Investigator will ensure that subject privacy and confidentiality of the subject's data will be maintained.

To protect privacy, every reasonable effort will be made to prevent undue access to subjects during the course of the study. Prospective participants will be consented in an exam room where it is just the research staff, the patient and his family, if desired. For all future visits, interactions

with research staff (study doctor and study coordinators) regarding research activities will take place in a private exam room. All research related interactions with the participant will be conducted by qualified research staff who are directly involved in the conduct of the research study.

To protect confidentiality, subject files in paper format will be stored in secure cabinets under lock and key. Subjects will be identified only by a unique study number and subject initials. Electronic records of subject data will be maintained using a dedicated compliant database, which is housed in an encrypted and password-protected file on a secure network drive. Access to electronic databases (without edit rights) will be limited to the Principal Investigator, the study coordinator, and the statistical team. The only personnel with both access and edit rights to the electronic databases are the data management team, including the clinical trials manager. Upon completion of the study, research records will be archived. Subject names or identifiers will not be used in reports, presentations at scientific meetings, or publications in scientific journals.

17.5 Records Retention

The Principal Investigator will maintain study-related records for the longer of a period of:

1. at least 2 years after the date on which a New Drug Application is approved by the FDA, if an IND is involved
2. at least 2 years after formal withdrawal of the IND associated with this protocol, if an IND is involved

17.6 Conflict of Interest

The Principal Investigator and Sub-Investigators must comply with applicable federal, state, and local regulations regarding reporting and disclosure of conflict of interest. Conflicts of interest may arise from situations in which financial or other personal considerations have the potential to compromise or bias professional judgment and objectivity. Conflicts of interest include but are not limited to royalty or consulting fees, speaking honoraria, advisory board appointments, publicly-traded or privately-held equities, stock options, intellectual property, and gifts.

40. US Department of Health and Human Services Food and Drug Administration Center for Drug Evaluation and Research (CDER). Acne Vulgaris: Establishing Effectiveness of Drugs Intended for Treatment Guidance for Industry. Rockville, MD: Office of Communications, Division of Drug Information. May 2018.
<https://www.fda.gov/downloads/Drugs/Guidances/UCM071292.pdf>

19 Appendix A: Patient Reported Outcome (PRO) Questions

Weekly Visit

1. How often are you applying the study drug?
 - Once a Day
 - Twice A Day
2. Did you apply the study product as instructed?
 - Yes
 - No
 - If no: clarify with comments
3. Would you like to apply the study drug more often?
 - Yes
 - No
4. Do you feel that your quality of life has improved from using the study drug?
 - Yes
 - No
5. How would you assess the change in your rash since your previous visit?
 - Worse
 - No change
 - A little better
 - Definitely better
 - Drastically better
 - Clear

**Clearing Questions- only to be asked if the Acne Vulgaris has cleared or partially cleared.
Indicate [] N/A if no clearing has occurred**

1. On approximately what date did the Acne Vulgaris clear?
2. Have any of your previously cleared lesion(s) come back? Yes/No
 - a. If Yes, on what date did it come back?
 - b. If Yes, where did it come back?
 - i. Same area as before
 - ii. New area, specify:

The following questions are for the last visit only

1. Do you feel that your quality of life has improved from using the study drug?
 - Yes
 - No

2. How would you assess the change in your rash since your previous visit?
 - Worse
 - No change
 - A little better
 - Definitely better
 - Drastically better
 - Clear

Clearing Questions- only to be asked if the rosacea has cleared or partially cleared.
Indicate [] N/A if no clearing has occurred

1. On approximately what date did the rosacea clear? _____

2. Have any of your previously cleared lesion(s) come back?

- Yes
- No

If Yes, on what date did it come back?

If Yes, where did it come back?

- Same area as before
- New area, specify:

Color Questions

1. Do you have any concerns about the color of the study product?
 - No concerns

- Mild concerns
- Major concerns

2. Did the study product stain (meaning the color stayed on after washing) your clothing/bedsheets, etc? Yes/No

20 Appendix B: Phone Follow-up Questions

1. What is the current status of your Acne?
2. Are you currently on any medications or treatments for controlling your Acne? If yes, obtain list.
3. Would you like to continue to use the study drug? Yes/No, Comments.

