6 STUDY OBJECTIVES

6.1 Primary Objectives

Part A

1. Determine whether the optimum frequency of topical application of BMX-010 0.03% is once per day or twice per day for a treatment interval of 7 to 28 days.
2. Determine whether the optimum frequency of topical application of BMX-010 0.1% is once per day or twice per day for a treatment interval of 7 to 28 days.
3. Determine if BMX-010 cream or gel provides better efficacy.
4. Evaluate the efficacy of BMX-010 0.03% in treatment of Acne Vulgaris.
5. Evaluate the efficacy of BMX-010 0.1% in treatment of Acne Vulgaris.

Part B

1. Evaluate the efficacy of BMX-010 compared to placebo in a randomized, double-blind trial.
2. Determine the percent of subjects showing a 2 grade improvement in IGA score after treatment with BMX-010 compared to Placebo.
3. Determine the percent of subjects showing a 2 grade improvement in IGA score with full or partial clearing (final IGA score of 1 or 0) after treatment with BMX-010 compared to Placebo.
4. Determine the time to full clearing of Acne Vulgaris after initiation of treatment with BMX-010.

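### The Appendix A clearing date does not separate full from partial clearing, so it cannot by itself serve Part B primary objective 4 (time to full clearing)

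*Protocol*

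**What the plan says.** **The objective.** In Protocol Section 6.1, Part B primary objective 4 is "Determine the time to full clearing of Acne Vulgaris after initiation of treatment with BMX-010". Objective 3, just before it, recognises two degrees of clearing: "full or partial clearing (final IGA score of 1 or 0". The natural reading is that IGA 0 is full clearing and IGA 1 is partial.

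**The form.** The weekly clearing block in Appendix A carries the instruction "Clearing Questions- only to be asked if the Acne Vulgaris has cleared or partially cleared". The not-applicable box is for "N/A if no clearing has occurred", so a partially cleared subject cannot be marked not applicable. The date item reads "On approximately what date did the Acne Vulgaris clear". Nothing on the form records whether the answer refers to full or partial clearing, and Appendix A does not tie partial clearing to an IGA grade. The last-visit block has the same structure but names another disease: "Clearing Questions- only to be asked if the rosacea has cleared or partially cleared".

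**Who decides clearing.** Sections 7.1 and 7.2 leave full clearing to the investigator, and Section 7.2.1 ties cleared to IGA 0. Table 4.a schedules the IGA at Days 8, 15, 22, 29 and 43, each within 2 days.

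**Sources of efficacy data.** Section 7 says Part B efficacy rests on IGA scores and patient-reported outcomes, without assigning a source to each objective.

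**The concern.** The protocol treats full and partial clearing as different outcomes, and one of its four Part B primary objectives is a time to the first of these. The only item that asks for a clearing date accepts both and does not label them. A subject at IGA 1 who answers as instructed leaves a clearing date on record although the acne has not fully cleared. Because the block is repeated at each visit, a subject who clears partially and then fully may give the earlier date again, and the form does not show which event is meant.

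If such dates were analysed as times to full clearing, both errors would run the same way: too many events, and some events too early. BMX-010 would appear to clear acne more often and faster than it does.

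**Working it through.** The protocol states no figure for this point, and Section 14.6 says the sample sizes have no statistical basis. The check is therefore mainly a comparison of passages.

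**1. Event wanted against event dated.**

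| | Objective 4 (Section 6.1) | Appendix A date item |
|---|---|---|
| Event | Full clearing | Full or partial clearing, not labelled |
| Judged by | Investigator, IGA 0 (Sections 7.2 and 7.2.1) | Subject, by recall |
| Resolution | Visit | Approximate calendar date |

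The two rows for event and judge do not match, so the item alone does not measure the objective.

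**2. What the visit schedule gives without the item.** From the days in Table 4.a:

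- Day 1 to 8, 8 to 15, 15 to 22 and 22 to 29: 7 days each.
- Day 29 to 43: 43 − 29 = 14 days.
- With windows of 2 days at both ends: at most 7 + 2 + 2 = 11 days and 14 + 2 + 2 = 18 days.

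First IGA 0 is therefore located to within these intervals whether or not the Appendix A date is used.

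**3. What unfiltered use would do.** Let p0 and p1 be the proportions with full and with partial clearing only. The share of dates that are not full-clearing events is p1/(p0 + p1). The protocol gives neither rate. With assumed ratios p1:p0:

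- 1:3 gives 1/4 = 25%
- 1:1 gives 1/2 = 50%
- 3:1 gives 3/4 = 75%
- 4:1 gives 4/5 = 80%

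The result only reflects the assumed ratio. The direction does not depend on it. As a constructed example of mis-dating, a subject who reports partial clearing at Day 8 and reaches IGA 0 at Day 29 would be dated 29 − 8 = 21 days early.

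**4. How far other data can repair it.** A date given at a visit with IGA 1 can be recognised as not full clearing. So can a date that falls before a later visit with IGA above 0. The subject's answer to weekly question 5, which offers clear as a separate response, gives a further check. Two things cannot be recovered: the date of full clearing for a subject who repeated the partial date, and whether a date lying between the last visit above IGA 0 and the first visit at IGA 0 marks partial or full clearing.

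**The case against.** A reader might infer that objective 4 will be analysed from the Appendix A date and that a primary objective is therefore biased. The documents do not support this. No section names that date as the variable for objective 4. Full clearing is the investigator's decision, IGA is scored at every scheduled visit on treatment and follow-up, and Section 11.1 makes IGA change from baseline through final follow-up an endpoint. Section 14 leaves the definition of analysis variables to an SAP that is not shown, so the choice of source and the handling of interval censoring are not missing from the protocol.

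Same-visit IGA and question 5 would also sort most of the dates. The broad trigger has a plausible purpose, because the block goes on to ask about recurrence of cleared lesions, which concerns partial clearers too. The trial is exploratory, and objective 4 names no comparator.

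All of that stands, and it limits the point. It does not remove it. An SAP can choose a source but cannot fully recover a label that the form never asked for. Use of the date is not excluded either: Section 7 counts patient-reported outcomes among the efficacy measures, and the synopsis criteria for evaluation mention the IGA only at baseline and end of study, which alone would give no time to clearing.

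**Conclusion.** The point holds as a defect of the form. The Appendix A date, in both the weekly and last-visit blocks, mixes full and partial clearing and cannot by itself serve objective 4. Unfiltered use would overstate the number of clearings and shorten the time to them, by an amount the protocol gives no rates to estimate. The 25% to 80% range rests wholly on assumed ratios and is not a finding about this trial.

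The objective itself is not lost. First investigator-scored IGA 0 can be derived to within nominally 7 days up to Day 29 and 14 days from Day 29 to Day 43. What the wording costs is a reliable date inside those intervals, and it leaves room for the wrong source to be used.

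The conclusion assumes that IGA 0 means full and IGA 1 partial clearing, as objective 3 implies. The descriptions of clear do differ. The synopsis scale requires no lesions of either type. Section 11.1 lists no papules, pustules or erythema at grade 0, yet its text allows residual erythema. Section 7.2.1 looks only to inflammatory signs.

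**What to change.** 1. In both Appendix A clearing blocks, add a field recording whether clearing is full or partial, and label the date accordingly, with separate full and partial dates. Keep the recurrence items for both groups.
2. In the last-visit block, replace the references to rosacea with acne vulgaris.
3. In Section 6.1, state that the event for objective 4 is the investigator's determination of full clearing (IGA 0), and that the subject's date is supportive only.
4. Reconcile the descriptions of clear in the synopsis IGA scale, Section 7.2.1 and Section 11.1, so that the event has one meaning.

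The cost is one extra form field and a few lines of text, with no added visit or procedure. How the visit interval is handled in the analysis can stay with the SAP.

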7 STUDY DESIGN

The purpose of this study is to first explore the optimum formulation (gel vs. cream), concentration (0.03% vs. 0.1%), and dosing frequency (QD vs. BID) of BMX-010 in subjects with Acne Vulgaris in Part A. In Part B, the optimal formulation, concentration, and frequency will be used to study the efficacy of BMX-010, as determined by IGA scores and PROs.

[figure not shown]

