8 SELECTION AND WITHDRAWAL OF SUBJECTS

8.1 Inclusion Criteria

1. Male or female, at least 18 years of age;
2. A clinical diagnosis of mild to severe facial Acne Vulgaris; Subjects may also have acne at other body sites;
3. Screening and Baseline IGA score ≥ 2 (greater than or equal to 2);
4. Willing to refrain from using any topical or systemic treatments for inflammatory skin disease, other than the investigational product;
5. Candidate for topical treatment of Acne;
6. If a cleanser, moisturizer or sunscreen is needed during the study, Subjects must be willing to use only allowed cleansers, moisturizers, sunscreens, or moisturizer/sunscreen combination products. If the subject wears makeup they must agree to use non-comedogenic makeup.
7. Females of child-bearing potential must have a negative urine pregnancy test within 48 hours prior to the first drug administration;
8. Females of child-bearing potential must be willing to use 2 methods of contraception deemed adequate by the investigator (for example, oral contraceptive pills plus a barrier method) through the trial and for 1 month thereafter to be eligible for, and continue participation in, the study;
9. Ability to complete the study in compliance with the protocol, including agreement in writing to apply study product only to the assigned areas; and
10. Ability to understand and provide written informed consent.

8.2 Exclusion Criteria:

1. Any underlying disease(s) or some other dermatological condition of the face that requires the use of interfering topical or systemic therapy or makes evaluations and lesion count inconclusive;
2. Use of androgen receptor blockers (such as spironolactone or flutamide);
3. Severe cystic acne, acne conglobata, acne fulminans, or secondary acne;
4. Use of phototherapy devices, energy-based devices, adhesive cleansing strips, or cosmetic procedures (e.g., facials, peeling, comedo extraction) in the past week;
5. Presence of beard or excessive facial hair at Screening which would interfere with the study treatments or study assessments and refusal to remove for duration of study;
6. Prior or current concomitant therapies that would interfere with assessments in the study;
7. Subjects with any underlying disease that the Investigator deems uncontrolled, and poses a concern for the subject's safety while participating in the study;

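### The last-visit patient questionnaire conditions its clearing and relapse questions on rosacea, while the weekly form names acne, the only disease studied

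*Protocol*

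**What the plan says.** Eligibility in Section 8.1 requires "A clinical diagnosis of mild to severe facial Acne Vulgaris"; no other indication is enrolled. Section 7 says that Part B will use the regimen chosen in Part A "to study the efficacy of BMX-010, as determined by IGA scores and PROs". The fourth Part B primary objective in Section 6.1 is "Determine the time to full clearing of Acne Vulgaris after initiation of treatment with BMX-010".

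Appendix A (Section 19) sets out the questions put to subjects, in a weekly set and a set reserved for the last visit. Each contains a clearing block with an opening condition, a not-applicable box for subjects without clearing, a date item, and items on whether, when and where lesions returned.

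- Weekly set: the block is "only to be asked if the Acne Vulgaris has cleared or partially cleared", and the date item is "On approximately what date did the Acne Vulgaris clear".
- Last-visit set: the block is "only to be asked if the rosacea has cleared or partially cleared", and the date item is "On approximately what date did the rosacea clear".

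Both sets also ask how the subject's *rash* has changed since the previous visit, in identical words.

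**The concern.** A stray disease name in a background paragraph does no harm to the data. Here it sits in the skip condition of an operative form and in the date question that follows it. The condition decides whether the remaining items in the block are asked at all, and the fallback entry is not applicable.

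A site that follows the text literally finds no rosacea to have cleared and ticks the box. A site that reads through the error asks about acne. With up to 20 centers, both are foreseeable. Once recorded, a not-applicable entry that arose from the wording looks the same as one from a subject whose acne never cleared. No later analysis rule can separate the two from this form alone.

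**Working it through.** No arithmetic is in dispute and the plan gives no figure to reproduce, so the check is a comparison of texts followed by a delimitation of what is exposed.

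**Item by item, Appendix A**

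| Item | Weekly set | Last-visit set |
|---|---|---|
| Condition for the clearing block | Acne Vulgaris | rosacea |
| Date of clearing | Acne Vulgaris | rosacea |
| Return of cleared lesions | no disease named | no disease named, but under the rosacea condition |
| Change since previous visit | rash | rash |

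Both disease-naming items in the last-visit clearing block are wrong, and both weekly counterparts are right. Nothing elsewhere in the protocol corrects or explains the difference. The Background (Section 5) also names rosacea as the target disease in one paragraph, which suggests text carried over from another protocol.

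**Which visits are exposed.** Table 4.a schedules the patient-reported questions on Days 8, 15, 22, 29 and 43. For a subject whose last visit is Day 43, the acne-worded weekly set covers the first four, and the last-visit set covers what happens after Day 29: 43 − 29 = 14 days, out of 43 − 1 = 42 days from baseline. For a subject who clears, stops treatment and is brought back the following week for the end-of-study visit, an option in Section 7.2.1, the last-visit set is the only later questionnaire that asks about relapse. This assumes that the last-visit set replaces the weekly set at that visit. Its repetition of the quality-of-life, change and clearing items points that way, but the protocol does not say so. If both sets were asked, the weekly block would supply the acne answer.

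**Which subjects are exposed.** Maximum enrolment is 60 + 150 = 210, and all of them meet the faulty form. The gated items apply only to subjects with full or partial clearing, so only those subjects can lose clearing or relapse answers. The protocol gives no expected clearing rate, so 210 (150 in Part B) is an upper bound and not an estimate.

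**Which data are not exposed.** IGA and facial lesion counts are scheduled at Days 29 and 43 independently of the questionnaire. The weekly clearing dates name acne. The color items and the quality-of-life item on the last-visit form do not depend on the condition.

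**The case against.** The strongest reply is that acne is the only plausible referent. Every subject has facial acne, exclusion criteria 1 and 10 remove other skin conditions that would confound evaluation, and the questions are put at clinic visits where staff know the indication. Most sites may simply read *acne*. That stands as a limit on the likely harm, but it does not remove the skip condition, and it relies on every site making the same silent correction.

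Three stronger readings are tempting, and the documents do not support them.

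- A reader might infer that the final clearing and relapse answers do not concern acne at all. The relapse item names no disease and asks about lesions that had cleared earlier; only the condition above it mentions rosacea. The supportable statement is that these answers may be missing or inconsistent.
- A reader might infer that the primary time-to-clearing objective is compromised. Appendix A is the only place that asks for a calendar date of clearing, but nothing in the protocol makes that date the source for the objective. Sections 7.2 and 7.2.1 place the judgement of clearing with the investigator, with IGA = 0 as the criterion.
- A reader might take Section 7 to mean that half of the efficacy evidence is at stake, because it describes efficacy "as determined by IGA scores and PROs". The Criteria for Evaluation in the Synopsis add lesion counts as a further measure, and no Part B objective names a patient-reported outcome.

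The *rash* wording is also not a last-visit fault. It is the same on both forms, so answers remain comparable across visits; it is loose wording for acne subjects and no more.

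Relapse by Day 43 would in addition show in IGA and lesion counts, and Section 7.2.1 tells subjects whose acne returns during the study to contact the center. What rests on this form alone is the subject's own account at the last visit, including the recalled date and site of relapse. The optional later contact in Appendix B asks about current status and does not ask for either.

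**Conclusion.** The inconsistency is real and wrong as written, with minor to moderate consequence. The last-visit clearing block is conditioned on, and dates, the clearing of a disease that the trial does not study, while the weekly block is correct. Among subjects with full or partial clearing, the last-visit clearing date and relapse answers may be recorded as not applicable or handled differently between sites, and such entries could not be separated afterwards from true non-clearing.

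The size cannot be put as a number from the protocol, because neither the clearing rate nor the way sites would act on the wording is given. The conclusion assumes that the form in use follows Appendix A and that the last-visit set replaces the weekly set at the final visit. No stated objective is shown to depend on the affected items.

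**What to change.** Before the form or eCRF is used, make four word replacements in Appendix A:

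1. In the last-visit clearing block, replace *rosacea* with *Acne Vulgaris* in the opening condition.
2. Make the same replacement in the date item of that block.
3. Replace *rash* with *acne* in the weekly change item.
4. Make the same replacement in the last-visit change item.

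Both forms then ask the same questions about the disease under study. The cost is a wording change to the form and the eCRF, with no effect on visits, sample size or procedures. If the form has already been used, the answers cannot be recovered by analysis. In that case, record which wording each site used and flag last-visit not-applicable entries made under the old text.
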